## **9 SAFETY**

During the entire duration of the study, all serious adverse events (SAEs) that may be causally related to the study intervention are collected and documented in source documents. Reportable events are recorded in the case report form (CRF). Study duration encompassed the time from when the participant signs the informed consent until the last protocol-specific procedure has been completed, including a safety follow-up period.

In order to guarantee participants' safety and health, further adverse events which must be documented or reported are to be designated in the protocol or at the request of the responsible CEC.

#### **Serious Adverse Event**

A serious adverse event is defined as any event which:

- requires inpatient treatment not envisaged in the protocol or extends a current hospital stay;
- results in permanent or significant incapacity or disability;
- is life-threatening or results in death; or
- causes a congenital anomaly or birth defect.

## 9.2 Recording and Assessment of Serious Adverse Events

The investigator has the responsibility for SAE identification, documentation, and assessing the causal relationship study intervention.

All SAEs will be fully documented in the appropriate eCRF. For each SAE, the investigator will provide the onset, duration, treatment required, outcome and action taken with regard to the study intervention.

The assessment by the investigator with regard to the study intervention relation is done according to the following definitions:

Unrelated	

• The event started in no temporal relationship to the medical intervention applied and

• The event can be definitely explained by underlying diseases or other situations.

Related	

• The event started in a plausible temporal relationship to the medical intervention applied and

• The event cannot be definitely explained by underlying diseases or other situations.

## 9.3 Reporting of Serious Adverse Events

If, in the course of a clinical trial, serious adverse events occur in participants in Switzerland, and it cannot be excluded that the events are attributable to the intervention under investigation, the investigator must report these events:

- to the CEC **within 15 days**.

### Safety and protective measures

If immediate safety and protective measures have to be taken during the conduct of this clinical trial, the investigator must notify the CEC of these measures, and of the circumstances necessitating them, **within 7 days**.

### Annual Safety Report

All SAEs will be summed up in the **annual safety report (ASR)** and submitted to the CEC. ASR shall contain:

- A summary of events including severity and causal relationship to the intervention and on the safety of participants.
- The accompanying letter provided with the Annual Safety Report should contain a short summary of the status of the clinical trial in Switzerland (number of centers open/closed, number of patients recruited/recruitment closed, and number of SAEs).

## 9.4 Follow up of (Serious) Adverse Events

Participants terminating the study (either regularly or prematurely) with

- reported ongoing SAE, or
- any ongoing AEs of laboratory values or of vital signs being beyond the alert limit

will return for a follow-up investigation. This visit will take place up to 30 days after terminating the treatment period. Follow-up information on the outcome will be recorded on the respective SAE page in the eCRF.

## 10 STATISTICAL METHODS

Categorical data will be tested for differences using Fisher's exact or chi-squared tests, as appropriate, whereas continuous variables will be tested using Wilcoxon rank sum tests.

### 10.1 Hypothesis

We hypothesize that PDT improves skin antisepsis by reduction of persistent skin colonizing bacteria by its bactericidal effects.

### 10.2 Determination of Sample Size

Aim: 20 volunteers to show the effect of PDT in healthy volunteers.

### 10.3 Planned Analyses

- As a pilot study, we plan to do descriptive statistics only.
- Categorical data will be tested for differences using Fisher's exact or chi-squared tests.
- Continuous variables will be tested using Wilcoxon rank sum tests.
- Data will be analyzed using Stata® version 14.2 (Stata Corporation, College Station, TX). Two-tailed P-values <0.05 are considered statistically significant.

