Inclusion / Exclusion criteria:	
Inclusion criteria  Healthy male and female participants <math>\geq 18</math> years who
 
 
volunteer for the pilot study in which a routine photodynamic treatment in the Department of Dermatology will be applied and effect of skin colonization will be analyzed, and
 
an informed consent is signed by the participant (after information about the project).
 
 
Exclusion criteria
 
 
Pregnant and lacting women
 
Participants with inability to follow the procedures of the study, e.g. due to language problems, psychological disorders, dementia, etc.,
 
Participants taking antibiotics in the 14 days prior to PDT or until follow-up at 21 days
 
Participants who received oral retinoid therapy within the last 6 months
 
Participants who received anti-inflammatory agents as NSAR within the 14 days prior and after the PDT
 
Participants taking any photosensitizing drugs within 4 weeks prior to PDT
 
Participants who had a history of photosensitivity disorder
 
Fitzpatrick's skin phototype V-VI
 

Study Intervention:	
 
Photosensitizer application, followed by PDT (1x)
 
Skin swabs on day 0, 1, 3, and 5
 
 
Group A: use of MAL induced Pp IX photosensitizer  Group B: use of Methylene blue photosensitizer

Reference Intervention:	Skin swabs before and after skin antisepsis in 10 participants without PDT from the contralateral side.
Number of Participants with Rationale:	Aim: 10 volunteers in group A and 10 volunteers in group B There will be only descriptive statistics to see if numbers of colonizing bacteria are decreased with PDT to plan a clinical trial in patients getting a hip joint arthroplasty and previous antisepsis.
Study Duration:	1 year
Study Schedule:	
 
Project start (FPFV): January 2021 
 
First participant: January 2021
 
Last participant: June 2021
 
 
 
Project end (LPLV): December 2021
 

Investigator(s):	[name] Division of Infectious Diseases and Hospital Hygiene University Hospital Zurich [name] Email: [contact] [contact]
Study Centre(s):	Single-center

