## Microbiology

In short, the patient's sample swabs will be streaked out onto Columbia sheep blood agar plate without antibiotics (bioMérieux, Marly-l'Etoile, France), colistin-nalidixic acid (CNA) blood agar (bioMérieux) plate for aerobic cultivation and a Brucella plate (in-house sheep blood agar plates with hemin and vitamin K1) for anaerobic cultivation using GENbag (bioMérieux). Final identification will be done by matrix-assisted laser desorption ionization-time of flight mass spectrometry spectrometry (MALDI-TOF MS) using a Bruker MALDI Biotyper. The amount of bacteria will be semiquantitative described as +, ++, +++ based on growth on agar plates. All cultured microorganisms will be stored in skim milk at -80C° for potential subsequent analysis by whole genome sequencing for analyzing the secondary outcome.

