#### 10.3.2 Primary Analysis

Descriptive comparisons of microbiological data before and after PDT by [name]

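### The growth grade is ordered, but section 10.3 assigns it no ordered test, and on the natural reading it goes to Fisher's exact or chi-squared, which ignore the order

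*Combined protocol and SAP*

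**What the plan says.** Section 4.1 makes bacterial density and species by culture the primary outcome. The Microbiology part of section 8.2.1 gives the only culture scale for density: "The amount of bacteria will be semiquantitative described as +, ++, +++ based on growth on agar plates". No growth is not listed as a level.

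The synopsis, section 10 and section 10.3 name two classes of data. For the first, section 10.3 has "Categorical data will be tested for differences using Fisher's exact or chi-squared tests", and section 10 has the slightly fuller "Categorical data will be tested for differences using Fisher's exact or chi-squared tests, as appropriate". For the second, section 10.3 has "Continuous variables will be tested using Wilcoxon rank sum tests". No test for ordered categories and no paired test is named, and the growth grade is placed in neither class.

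On the status of testing, section 10.3 opens with "As a pilot study, we plan to do descriptive statistics only", yet the same list names the tests and ends with "Two-tailed P-values <0.05 are considered statistically significant". Section 10.3.2 gives the primary analysis as "Descriptive comparisons of microbiological data before and after PDT by" a named person. The synopsis sets the group sizes: "Aim: 10 volunteers in group A and 10 volunteers in group B". Section 10.2 gives no effect size or power.

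**The concern.** A three- or four-step grade is not a continuous variable, so a reader applying section 10.3 would most naturally send it to Fisher or chi-squared. Those tests treat the grades as interchangeable labels. The hypothesis in section 10.1 is that photodynamic therapy (PDT) reduces persistent colonising bacteria, which is a shift down the scale. A test that cannot see direction along the scale discards information relevant to that hypothesis, in a trial with 10 participants per group.

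If the categorical reading is rejected instead, the test for the primary density measure is simply unspecified and would be chosen with the data in view. Either way, p-values judged at 0.05 may be reported from this pilot, and its results inform whether an arthroplasty trial is planned (sections 2.1 and 5.1).

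**Working it through.** The plan states no power or effect size, so it has no figure of its own to reproduce.

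**Inputs from the documents.** 10 participants in each of A and B (synopsis); grades +, ++, +++ (8.2.1); two-sided 0.05 (10.3).

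**Assumed inputs.** No growth is added as a lowest fourth level. The grade distributions are assumed, because the documents give none.

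**Tests.** Let a_k be the count at grade k in A and t_k the count in both groups together. Given the totals, a table has probability Π C(t_k, a_k) / C(20, 10).
- Fisher (4 × 2): p is the summed probability of all tables no more likely than the one observed.
- Exact rank-sum: mid-rank m_k = (number below grade k) + (t_k + 1)/2; W = Σ a_k m_k, with expectation 10 × 21/2 = 105; p = P(|W − 105| ≥ |w − 105|).

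**One worked table (none/+/++/+++).** A = 4/4/2/0, B = 1/2/4/3. Totals are 5/6/6/3 and mid-ranks 3, 8.5, 14.5, 19. W = 12 + 34 + 29 = 75, against 105 expected. Fisher p = 0.13; exact rank-sum p = 0.024.

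Now swap the labels none and ++: A = 2/4/4/0, B = 4/2/1/3. Fisher is unchanged at 0.13. Mid-ranks become 3.5, 9.5, 15, 19, so W = 7 + 38 + 60 = 105 and the rank-sum p is 1.0. Fisher cannot tell an ordered shift from a reshuffle.

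**Power for A versus B.** Each group has C(13, 3) = 286 possible results. Power is the total multinomial probability of those of the 286 × 286 pairs with p below 0.05.

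| One group (none/+/++/+++) | Other group | Fisher | Exact rank-sum | Gain (points) |
|---|---|---|---|---|
| .6/.2/.1/.1 | .2/.3/.3/.2 | 32.7% | 38.5% | 5.8 |
| .7/.2/.1/0 | .2/.3/.3/.2 | 51.2% | 68.8% | 17.6 |
| .8/.2/0/0 | .3/.3/.3/.1 | 54.3% | 69.0% | 14.7 |
| .5/.3/.2/0 | .1/.2/.4/.3 | 54.0% | 74.7% | 20.7 |
| .4/.3/.2/.1 | .1/.2/.3/.4 | 33.5% | 49.5% | 16.0 |

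With equal distributions both tests reject about 4% of the time, so the gain is not bought with excess false positives.

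**Limits.**
- One arm wholly sterile: both tests reject when at least 5 of 10 in the other arm show growth. If half are expected to grow, power is P(Bin(10, 0.5) ≥ 5) = 638/1024 = 62.3% for each. Gain 0.
- Three levels only: the exact gain over Fisher is about 1 to 7 points (four assumed control distributions, odds ratios 3 to 20).
- Four levels, proportional-odds shifts, each control level at least 10%, odds ratios 2 to 20: median gain over Fisher 9 points, maximum 18.
- Not a shift: for .4/.1/.1/.4 against .1/.5/.3/.1, Fisher has 62.5% and the rank-sum 7.3%.

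**Which comparison this covers.** The calculation needs independent groups, so it describes A versus B only. Before/after is within participant, and the control is the same participant's other groin (section 2.5). No paired power was calculated.

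**The case against.** The strongest reply has four parts.

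First, the plan never states that the grade is categorical. Section 10 adds a qualifier about appropriateness, and the rank-sum test is already listed. A reader might infer that the plan commits the grade to order-blind tests; the text supports only that it names no class, with categorical the likelier reading. This part stands.

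Second, the analysis is described as descriptive in the synopsis, 10.3 and 10.3.2. A reader might infer that the trial forfeits some 20 points of planned power. No power was planned, so that does not follow. The reply does not remove the point, because the same section prescribes tests and a significance threshold.

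Third, A versus B is sequential and non-randomised (5.1) and is not the stated primary analysis. So the power figures do not describe the primary comparison. The missing ordered test does affect it, because the tests listed ignore order within participants as well, and the pairing besides.

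Fourth, the previous pilot reported complete sterilisation, and section 2.4 ties going ahead to sterile cultures, a yes/no result for which Fisher is suitable between groups. In that case the gain is nil, as shown. But the previous pilot used a 635 nm source, whereas here MAL is activated by daylight and methylene blue is new. Scrapings before antisepsis and on days 1, 3 and 5 could also spread over the grades. The documents do not settle which pattern will occur.

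**Conclusion.** The point holds as a gap in specification with a clearly better choice available. The culture measure of density is ordered, no ordered test is assigned to it, and the natural reading of 10.3 sends it to tests that cannot use the direction of change.

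The size is modest and rests on assumptions. For A versus B at 10 versus 10 with four levels, the exact rank-sum gains about 6 to 21 points over Fisher in the five assumed shifts, and 0 when one arm is wholly sterile. The added no-growth level and all the distributions are assumptions. The figures should not be cited for the paired comparisons or as a loss against any target in the plan. The change is worth making before the data are seen; it does not call the design into question.

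**What to change.** Add to section 10.3, and align section 10 and the synopsis:

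*The growth grade is scored 0 (no growth), 1, 2, 3 and analysed as ordered: exact Wilcoxon rank-sum with mid-ranks for A versus B; exact Wilcoxon signed-rank (or sign) test for before/after and for treated versus contralateral groin in the same participant. Fisher's exact test is used only for yes/no variables compared between groups, such as any growth in A versus B; McNemar's exact test is used for these within participant. The number at each grade is reported.*

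Choose between signed-rank and sign test now. The signed-rank test ranks the differences between scores, while the sign test needs only the order. Add no growth to the scale in 8.2.1, and say in 10.3 whether the p-values are exploratory.

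The cost is a few sentences, with no extra samples or visits; confirm that the software version named in 10.3 gives exact p-values with ties. There is one small downside: a rank test has little power for a change in grades that is not a shift up or down. That is not the hypothesis here, and the table of counts at each grade would show such a pattern.

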Statistical Considerations:	Categorical data will be tested for differences using Fisher's exact or chi-squared tests, as appropriate, whereas continuous variables will be tested using Wilcoxon rank sum tests.
GCP Statement:	This study will be conducted in compliance with the protocol, the current version of the Declaration of Helsinki, the ICH-GCP as well as all national legal and regulatory requirements.

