## 2.5 Explanation for Choice of Comparator Intervention

We will use for our control group without PDT the contralateral groin of the same participants (no further participants needed).

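### The before/after and treated/contralateral comparisons are paired, but the plan names only independent-sample tests and ties none of them to a comparison

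*Combined protocol and SAP*

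**What the plan says.** The tests are chosen by variable type only. Section 10 gives Fisher's "exact or chi-squared tests, as appropriate, whereas continuous variables will be tested using Wilcoxon rank sum tests", the synopsis (Statistical Considerations) repeats that "continuous variables will be tested using Wilcoxon rank sum tests", and section 10.3 says the same: "Continuous variables will be tested using Wilcoxon rank sum tests". Section 10.3 also states "As a pilot study, we plan to do descriptive statistics only" and then "Two-tailed P-values <0.05 are considered statistically significant".

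The comparisons are described elsewhere. Section 10.3.2 defines the primary analysis as "Descriptive comparisons of microbiological data before and after PDT". Section 2.5 defines the comparator: "We will use for our control group without PDT the contralateral groin of the same participants". Section 5.2 and the footnote to its flow chart agree that the control is the other leg of the treated person. The hypothesis in section 10.1 is that PDT lowers the number of persisting skin bacteria.

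The culture outcome is a grade. Under Microbiology in section 8.2.1: "The amount of bacteria will be semiquantitative described as +, ++, +++ based on growth on agar plates". The plan does not say whether this grade counts as categorical or continuous.

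**The concern.** Before/after uses the same groin of the same person, and treated/contralateral uses two groins of the same person. Fisher, chi-squared and rank sum tests all assume that the two sets of values come from different people. They suit group A versus group B with one value per person. Applied to the other two comparisons, they discard the within-person change that the own-groin control was chosen to show.

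At stake are the estimate, interval and p-value for the study's own hypothesis. Sections 2.1 and 2.4 make these results the basis for deciding on a larger trial, and section 10.3 sets a threshold for calling them significant.

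**Working it through.** **Step 1: comparisons against named tests.** Section 10.2 gives a target of 20 with no power, effect size, SD or rate, so there is no figure to reproduce.

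| Comparison | Structure | Test tied to it in the plan |
|---|---|---|
| Before vs after PDT (10.3.2) | paired | none |
| Treated vs contralateral groin (2.5, 5.2) | paired | none |
| Group A vs group B | independent, if one value per person | none |

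**Step 2: growth yes/no.** The tables are illustrative, with 10 pairs (one group).

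*8/10 with growth before, 2/10 after.* Fisher: 2 × (45×45 + 10×10 + 1)/C(20,10) = 4252/184756 = 0.023, whatever the pairing. Exact McNemar depends on the number losing growth (b) and gaining it (c), with b − c = 6: p = 2 × Σ C(b+c, i)/2^(b+c), summed over i = 0 to c.
- c = 0, b = 6: 2/64 = 0.031
- c = 1, b = 7: 2 × (1+8)/256 = 0.070
- c = 2, b = 8: 2 × (1+10+45)/1024 = 0.109

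The paired standard error of the difference of 0.60, √(b + c − (b−c)²/n)/n, is √2.4/10 = 0.155, √4.4/10 = 0.210 and √6.4/10 = 0.253 in the three cases. The unpaired one is always √(2 × 0.8 × 0.2/10) = 0.179. Under independence 1.6 people would show growth both times; the three cases have 2, 1 and 0. So only c = 0 shows positive association, and there both tests fall below 0.05.

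*5/10 before, 0/10 after.* Fisher: 2 × 252/15504 = 0.033. McNemar: 2/2⁵ = 0.0625.

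*20 pairs, 14 before and 8 after, 6 losses and no gains.* Fisher 0.111; McNemar 2/2⁶ = 0.031. The disagreement can therefore go either way.

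**Step 3: the grade.** The documents give no correlation or grade distribution, so all inputs are assumed: 10 pairs, a latent bivariate normal cut at its quartiles into 0/+/++/+++, and a shift of 0 or 1 SD (60,000 simulated datasets per cell; 15,000 for exact tests). The interval row uses mean grade scored 0 to 3, for illustration only.

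| Assumed correlation | 0.3 | 0.5 | 0.7 |
|---|---|---|---|
| Rank sum type I error (nominal 5%) | 2.4% | 1.2% | 0.3% |
| Paired/unpaired 95% CI width at 1 SD | 1.74/1.86 = 94% | 1.56/1.86 = 84% | 1.36/1.86 = 73% |
| Power, exact rank sum | 42% | 42% | 42% |
| Power, exact signed-rank (Pratt) | 41% | 47% | 58% |
| Power, approximate rank sum | 48% | 48% | 48% |
| Power, approximate signed-rank (Pratt) | 54% | 65% | 80% |

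At correlation 0 pairing loses: exact power is 34% for signed-rank against 44% for rank sum, and the paired interval is 106% as wide.

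**Step 4: exact or approximate.** Take 4 improved by one grade and 6 unchanged. With zeros kept, the four non-zero ranks are each (7+8+9+10)/4 = 8.5. The rank sum is 34, its null mean 17 and SD √(4 × 8.5²/4) = 8.5, so z = 2.0 and p = 0.0455. The exact p-value is 2/2⁴ = 0.125. Much of the apparent power gain in step 3 comes from the approximation.

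**Step 5: many zeros.** Suppose 5% growth on the treated side and 50% on the contralateral side after antisepsis. Exact signed-rank power is 31%, 31% and 35% at correlation 0.3, 0.5 and 0.7, against 50%, 48% and 49% for exact rank sum. If 95% show growth before PDT and 5% after, the approximate versions of both tests have 99.6% to 100% power.

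**The case against.** The strongest reply is that this is a pilot. The synopsis (Number of Participants), section 10.3 and section 10.3.2 all call the analysis descriptive, and a descriptive before/after summary needs no test. The named tests may be meant for group A versus group B, a real aim of the study. Part of this stands: a reader might infer that the plan orders a rank sum test for before/after, and the text does not say so. What does not stand is that the label removes the problem. Section 10.3 goes on to say data will be tested and sets a 0.05 rule. No other test is offered for the hypothesis in section 10.1, and paired descriptive summaries are not specified either.

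A second reply is that the power gain depends on assumptions. This also stands. With exact tests at 10 pairs it is absent or small at low correlation, and it turns into a loss when most grades are 0. If the complete sterilization reported for the earlier pilot (section 2.1) recurs, the choice of test hardly affects before/after.

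Two other strong readings are not supported. One is an inflated false-positive rate: under positive correlation the rank sum test is conservative. Inflation would need negative correlation (6.9% at −0.3 with continuous normal data, 10 pairs), which the documents give no reason to expect. The other is that the sample size is invalid: the target of 20 rests on no power calculation.

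**Conclusion.** The point holds as a mismatch between design and named methods that should be fixed. It is not a wrong test expressly assigned. If section 10 is applied to the paired comparisons, the p-values and intervals ignore the pairing. Under positive correlation the rank sum test rejects too rarely (2.4% to 0.3% in place of 5% at correlation 0.3 to 0.7), and a paired interval would be 94% to 73% as wide as the unpaired one. Fisher and McNemar can fall on opposite sides of 0.05 in either direction.

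The binary figures are exact for the tables shown, but the tables are illustrative. The grade figures rest on assumed correlations and distributions. No firm power gain is claimed. The main benefit is a correct paired estimate, interval and p-value for planning the next study.

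**What to change.** In sections 10 and 10.3 and the synopsis:

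1. For before/after PDT within each group, and for treated/contralateral where contralateral swabs are planned, report the numbers improved, unchanged and worse on the 0/+/++/+++ grade (0 being no growth). Report also the paired difference in the proportion with growth, with a 95% CI. If p-values are given, use the exact Wilcoxon signed-rank test with zeros kept (Pratt) for the grade and exact McNemar for growth yes/no.
2. Keep Fisher and rank sum for group A versus group B, with one value per person.
3. Label all p-values exploratory, or delete the 0.05 rule, to agree with the descriptive aim.

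The change is wording only and adds no swabs. The cost is that some p-values become less favourable: exact McNemar needs at least 6 discordant pairs for p below 0.05 (2/2⁵ = 0.0625; 2/2⁶ = 0.031). Exact signed-rank can lose power at low correlation or when most post-treatment grades are 0.

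Separately, the number of contralateral controls must be reconciled before that comparison is specified. The synopsis says 10 participants, section 5.2 says all, and section 7.1.2 says the first 10. Since section 2.7 puts the first ten in group A, the last reading leaves group B with no controls.
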